Rationale for PPJ. *Why combine daily life review (including gratitude interventions) with planning for the future (activity scheduling) in a daily exercise?* Gratitude interventions and activity scheduling should reinforce and extend each other’s impact. A positive correlation between higher levels of gratitude and greater behavioral activity have been reported.^{29,30} This association may be causal: in previous research, gratitude has been shown to improve affect^{17,31} which has been shown to encourage more frequent and more diverse types of activity.³² Therefore, gratitude intervention should encourage positive, abstinent behavior. Conversely, activity scheduling will enhance gratitude by guiding individuals to shape

their own positive experiences rather than to passively notice them.

Positive behaviors will produce content to populate the next day's gratitude inventory.

3. The next phase of this study will add to the existing knowledge base because we will collect more information about PPJ's feasibility, acceptability and impact with a larger sample size. Our development study included only women; this phase of the study will include women and men. We will also have a control group in this next phase of the study. We will also modify the protocol so we can conduct the study on Zoom to comply with shelter-in-place orders and COVID19 best practices Study Endpoints/Events/Outcomes

- 3.1. Primary Endpoint/Event/Outcome: The primary outcome is empirical data on the feasibility and acceptability of PPJ. We will also assess rates of substance use and treatment retention as primary outcomes.
- 3.2. Secondary Endpoint(s)/Event(s)/Outcome(s): These include hypothesized mediators of the effect of the intervention on outcomes. These include: mood, satisfaction with life, commitment to sobriety, alcohol and drug craving, anxiety, and depression. For a complete list, see the measures section 5.2.

4. Study Intervention(s)/Interaction(s)

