Secondary measures: outcomes and mediators. We will compare rates of treatment retention and recurrence of substance use to the general rates reported by NUWAY. We will also examine pre-post treatment means and standard deviations of hypothesized mediators (affect, satisfaction with recovery, individual items theoretically related to PPJ) to determine if change is in the expected direction. We will also study these constructs to determine if there is reasonable variability in the data we collect or if floor or ceiling effects are present. We may also use single-subject designs⁵⁶ to depict change over time in key constructs by study participant. Qualitative data will be thematically analyzed using the techniques recommended by Braun and Clarke.¹³ Here, the researcher examines transcripts of texts and identifies key themes and how themes relate to one another. These data will inform intervention development and study implementation procedures.

Data analytic techniques to compare treatment and control groups. While this pilot study will not be adequately powered to detect significant effects between treatment and control groups, we will compare differences between the treatment and control groups at baseline and over time using either t-tests or multi-level modeling. T-tests will reveal significant differences between groups and multi-level modeling will show whether rate of change is significantly different between groups.

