If participants leave NUWAY on good terms during the study period, they may still be able to continue to be in the study because it is possible to continue study activities from outside of NUWAY for the independent practice phase. Any smartphone or tablet can be used to continue to participate in the independent practice phase. We may reach out to participants who continue to participant in this way to encourage them to continue in the study or ask if they wish to remain in the study using the contact information they provide to use through NUWAY Inc.

Follow up Interview: At approximately 30 days after the exit interview, we will follow up with participants. Zoom is the first choice but a telephone interview is acceptable for this procedure. We will ask participants about any substance use and journaling in the past 30 days. We will ask a few additional qualitative questions such as what was most memorable about being in the research study, and other similar questions. Participants will be encouraged to complete their final Qualtrics survey before this interview.

- 5.4. Individually Identifiable Health Information: Research study staff will meet with NUWAY staff at reasonable intervals to collect data on our primary outcomes: 1) treatment retention and 2) recurrence of substance use. At these occasions we will go through our list of study participants and ask NUWAY staff if: 1) that person has left treatment or been asked to leave; 2) that person has had a positive urine analysis screening indicating recurrence of substance use. We will mark down the replies in our deidentified data file. If the participant cannot remember date of entry into NUWAY, we will also gain this information from NUWAY staff and the treatment record. To facilitate this work, study staff will use a password-protected file linking participants' real names with study IDs (codenames/numbers).

6. This study therefore includes PHI and therefore we have combined our informed consent document with the appropriate text from a HIPAA authorization form.

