13.1. Withdrawal Circumstances: Participants will be withdrawn from the research without their consent for three reasons: 1) if the participant leaves NUWAY treatment against staff advice, 2) if the participant leaves NUWAY treatment at the request of staff for breaking the rules (for example, if they instigate a physical altercation), or 3) the participant leaves NUWAY treatment without discussion with staff and does not return. In these three situations, we would retain the person's data to date and code them as having discontinued treatment, since treatment retention is one of our primary outcomes. Participants of course can keep any Target gift card credits they have earned. If a participant leaves treatment and the study owes the individual Target gift cards, these will be distributed electronically.

13.2. Withdrawal Procedures: Participants can elect to leave the study at any time. This is emphasized in the informed consent document. If participants leave the study, we will still consult NUWAY records to determine relapse or

treatment departure for all study participants. We will include this information in the informed consent document.

Termination Procedures: If a participant stops participating in study activities, we will reach out to them up to 2 times and ask them if they would like to leave the study. If they say no then the process will stop and we will pay them any Target gift cards we owe them. If they are uncertain, we will warmly invite them to return to study activities, but will then consider them to have left the study if they do not return. We may also ask NUWAY staff to help us find out this information. If a person wishes to leave the study, we will note this in our study records. For individuals who leave the study prematurely, we will use data already collected and follow up data on relapse and treatment departure in our data analyses. Participants of course can keep any Target gift card credits they have earned and we will pay out any additional Target gift cards earned upon their exit from the study.

NUWAY study participants will be required to sign a release of information naming research staff, so that research staff and NUWAY staff can communicate with each other. If study participants call research staff by telephone, we will be able to call them back at NUWAY and speak to them or leave a message.

14. Risks to Participants

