17.2. Power Analysis: Preliminary data from existing behavioral activation (BA) research was used to determine power for the original proposal with N=76. For the outcome of abstinence (yes/no), previous work found outcomes for this variable of 41.5% for the BA group and 24.8% in the control group.¹⁴ For a 1-tailed test with $p < .10$, our power to detect a significant effect for abstinence (yes/no) in the proposed study would be .61 (for a 2-tailed test with $p < .05$, power would be .34). For the outcome of treatment retention (yes/no), previous work showed 96.6% for the BA group and 75.9% in the control group.¹⁶ For a 1-tailed test with $p < .10$, our power to detect a significant effect for treatment retention (yes/no) in the current study would be 94% (for a 2-tailed test with $p < .05$, power would be .82). Therefore, we should be adequately powered to detect statistically significant differences for the outcome of treatment retention in the current study using a 2-tailed test. R was used to conduct these power analyses.⁶¹

17.3. Statistical Analysis: This pilot study will not be adequately powered to detect an effect. Still we will compare the treatment and control groups using t tests and multi-level models to determine differences in means and in slopes between the groups, respectively. Descriptive statistics of the quantitative measures will be used to conduct power analyses and sample size calculations for a larger controlled trial. Also, multi-level analyses will

be conducted to determine significant change over time in factors of interest. We will also be able to examine whether change over time varied by certain subgroups (e.g., those with lower versus higher levels of the factor of interest at baseline).

17.4. Data Integrity: The use of Qualtrics to collect survey data will improve data accuracy because this allows us to avoid keystroke and other errors involved with manual data entry from written questionnaires. We will scrutinize the data produced by Qualtrics to ensure its integrity; whether values are within scale ranges and whether missing data is coded correctly. We will carefully examine and clean the data to ensure accuracy. For standardized instruments, we will be very careful to follow the directions for summing or taking the mean of scale items and reverse code any items as per the instructions.

18. Confidentiality

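### Section 17.2 calls the study adequately powered for treatment retention, sections 5.2 and 17.3 say it is not powered for between-group effects, and retention's status and test are unsettled

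*Combined protocol and SAP*

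**What the plan says.** **Power.** Section 17.2 bases its calculation on the original proposal's N=76. For retention it takes 96.6% vs 75.9% from earlier behavioral activation research and reports power of .82 (2-tailed, .05) and 94% (1-tailed, .10). It concludes that "we should be adequately powered to detect statistically significant differences for the outcome of treatment retention in the current study using a 2-tailed test". It names the software but no test. Section 17.3 then opens with "This pilot study will not be adequately powered to detect an effect". The paragraph in 5.2 on comparing the arms begins "While this pilot study will not be adequately powered to detect significant effects between treatment and control groups". Neither sets retention apart.

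**Status.** Section 3.1 says "We will also assess rates of substance use and treatment retention as primary outcomes". Section 5.4 speaks of meeting site staff to "collect data on our primary outcomes: 1) treatment retention and 2) recurrence of substance use". Section 13.1 explains how withdrawals are coded "since treatment retention is one of our primary outcomes". The 5.2 analysis plan, to which 17.1 refers the reader, has "Secondary measures: outcomes and mediators. We will compare rates of treatment retention and recurrence of substance use to the general rates reported by NUWAY".

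**Between-arm method.** Section 5.2 will compare "treatment and control groups at baseline and over time using either t-tests or multi-level modeling", and 17.3 ties these methods to means and slopes. No test is named for a yes/no outcome.

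**Sample size.** Section 11.1 now gives about 100 participants to be consented. Under item 11 of the screening steps in 9.3, people eligible only for the wait list also sign the main consent, so the number consented may exceed the number randomized.

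**The concern.** A reader who finishes 17.2 expects a powered comparison of retention between arms. A reader who finishes 17.3 or 5.2 expects none. Since retention also changes between primary and secondary, the plan does not fix how a between-arm retention result should be read. A null result could be presented as a powered negative or set aside as an underpowered pilot finding. A positive one could be presented as primary or secondary. Either choice could be made after the data are seen.

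The adequacy statement also rests on one pair of rates and a superseded N, with no indication of how far power moves if either rate differs. No success rule depends on it, so what is at stake is interpretation and reporting, not the conduct of the trial.

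**Working it through.** **Inputs from the documents.** N=76; retention 96.6% vs 75.9%; abstinence 41.5% vs 24.8%; stated powers .82 and 94% (retention), .34 and .61 (abstinence), all in 17.2. About 100 to be consented (11.1).

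**Assumptions not in the documents.** 1:1 allocation, so 38 per arm at N=76; 50 per arm only if all 100 are randomized; everyone analysed; no allowance for clustering by journaling group. The alternative rates in step 4 are illustrative.

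**Step 1. Reproduce the plan's figures.** Arcsine method: h = |2·asin(√p1) − 2·asin(√p2)|; power = Φ(h·√(n/2) − z), with z = 1.960 (2-tailed .05) or 1.282 (1-tailed .10).

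- Retention: h = 2.7707 − 2.1153 = 0.6554; h·√(38/2) = 2.857. 2-tailed: Φ(0.897) = .815 (stated .82). 1-tailed: Φ(1.575) = .942 (stated 94%).
- Abstinence: h = 1.4000 − 1.0426 = 0.3574; h·√(38/2) = 1.558. 2-tailed: Φ(−0.402) = .344 (stated .34). 1-tailed: Φ(0.276) = .609 (stated .61).

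All four figures reproduce.

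**Step 2. Update N at the same rates.** h·√(50/2) = 3.277; Φ(1.317) = .906. The planned increase raises power.

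**Step 3. Does the test matter?** Power at 96.6% vs 75.9%, 2-tailed .05. All rows except arcsine are by exact enumeration of the two binomials.

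| Test | 38 per arm | 50 per arm |
|---|---|---|
| Arcsine formula | .815 | .906 |
| Pearson chi-square | .821 | .908 |
| t-test on 0/1 data | .821 | .900 |
| Fisher exact | .682 | .822 |
| Yates-corrected chi-square | .647 | .822 |

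The test matters for reaching .80 only with Fisher or Yates, and only at N=76.

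**Step 4. Do the rates matter?** Arcsine, 2-tailed .05.

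| PPJ vs control | h | 38 per arm | 50 per arm |
|---|---|---|---|
| 96.6% vs 75.9% (section 17.2) | 0.655 | .82 | .91 |
| 96.6% vs 80% (illustrative) | 0.556 | .68 | .79 |
| 90% vs 75.9% (illustrative) | 0.383 | .39 | .48 |

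Dependence on the rates persists at 50 per arm.

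**Step 5. Precision.** The expected 95% CI half-width for the difference at 50 per arm and the plan's rates is 1.96·√((.966×.034 + .759×.241)/50) = 1.96·√(.2158/50) = .129, about 13 percentage points.

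**The case against.** **Scope.** The strongest defence is that 17.2 makes a specific statement about retention, while 5.2 and 17.3 give general pilot caveats followed by methods for continuous measures. That reading is possible and may be what was meant. It is not written, however: 5.2 refers to effects between the arms without limit, and 17.3 to any effect.

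**The conditions are visible.** The retention rates, alpha and power come just before the 17.2 conclusion, and N=76 opens the paragraph. This stands. Only the closing sentence drops the conditions, so a reader of the whole paragraph is not misled about where .82 comes from.

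**The old N is conservative.** This also stands: at the stated rates, 50 per arm gives more power.

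**Stronger readings that the documents do not support.**
- A reader might infer that .82 is a miscalculation. It is not (step 1).
- A reader might infer that adequacy hinges on the unnamed test. Pearson and the t-test, the latter being the between-arm method the plan does name, both keep .82 at 38 per arm. Fisher and Yates fall short there, but not at 50 per arm.
- A reader might infer that the borrowed rates are wrong, because 73.3% of the development study's participants were discharged on good terms (2.2). That study was single-arm, with 15 women at a residential site, and cannot settle the point. Section 2.3 openly hypothesizes benefits similar to behavioral activation.
- A reader might infer that no between-arm comparison of retention is planned. The general comparison paragraph in 5.2 may cover it; the gap is that it is not specified.

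**Conclusion.** The concern holds as an inconsistency in the current text. Section 17.2 claims adequate power for retention; 5.2 and 17.3 deny it for between-group effects without exception. Retention is primary in three sections and secondary in the analysis plan, where its only specific comparator is the site's general rate and not the randomized control arm.

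The .82 is correct for N=76 at 96.6% vs 75.9%, and becomes about .91 if 100 are randomized 1:1. It does not carry over to less favourable rates: a PPJ rate of 90% leaves .39 to .48, and a control rate of 80% leaves .68 to .79. These sizes rest on the assumptions listed with the calculation.

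The matter should be corrected, but it is modest. The main objective is feasibility, acceptability and logistics, and the plan already warns about limited power.

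**What to change.** 1. **Make 5.2, 17.2 and 17.3 agree.** Two routes are equally consistent, and the documents do not decide between them. One is to withdraw the adequacy sentence and treat the between-arm retention comparison as exploratory. The other is to write the retention exception into 5.2 and 17.3, and to state in the 17.2 conclusion that adequacy is conditional on 96.6% vs 75.9%, the N and the test.
2. **Restate the power in 17.2** for the number expected to be randomized (about 50 per arm only if all 100 are randomized 1:1), with one or two alternative pairs of rates. A full grid is optional.
3. **Give retention one status** in 3.1, 5.2, 5.4 and 13.1. In 5.2, compare it between the randomized arms with a named test for a yes/no outcome, reported as a difference with a 95% CI. Keep the site's general rate as context only.

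Cost: wording in a few places and a few extra power figures. No further participants or data are needed. The adequacy claim is either withdrawn or becomes conditional.

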We will use REDCap software to collect and organize study data including information collected on the screening check list, recruitment and enrollment and retention data, group attendance, study participation, exit interview, and follow up interview data. We will also obtain consent signatures electronically using REDCap.

Please note that the wording described in all participant-facing documents and questionnaires may be modified slightly to improve word choice or correct typos or other errors.

We will use Zoom features such as sharing our screen, white board, polls, and waiting room to enhance learning and protect integrity of group sessions.

We will teach basic Zoom skills (how to raise your hand, how to use the chat box, etc.).

5.

5.2. **Procedures.** This study will be advertised to be a study of “journaling in recovery from addiction.” All those interested in the study will be screened first by NUWAY staff to see if they meet basic criteria (see “prescreening guide for NUWAY staff,” attached) and then by research staff (using Zoom for electronic administration, see screening procedures, below). After screening and administration of the baseline assessment battery, individuals will be randomized into treatment and control groups using randomly generated pairs of numbers or using REDCap’s randomization procedure.

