To aid the treatment group in accessing the correct URL for uploading the photo of their journal and completing the Qualtrics questionnaire, the QR Code and the URL to the Qualtrics survey will be printed on a front page of the journal.

Please note, if any participant has technological difficulties with Zoom or with study procedures that we cannot adequately address during group sessions, we might place the participant with a research assistant in a Zoom break out room or make an appointment to meet with that participant by Zoom or telephone to help solve the difficulty.

See the table below for a summary of study activities by arm.

Study Activities by Arm

Baseline: All participants	Randomization	Phase 1. First 2.5 weeks	Phase 2. Following 2 weeks	Exit interview, immediately following Phase 2	Follow-up interview, approximately 1 month later
Screening and assessment battery All participants continue with treatment as usual at the host setting throughout this study	Control Group Treatment Group	Complete Qualtrics surveys 3-4 times a week, Earn gift cards This is the “group phase.” Attend approximately 8 hours of journaling groups. Complete Qualtrics surveys 3-4 times a week. Earn gift cards.	Complete Qualtrics surveys daily. Earn gift cards. This is the “independent practice phase.” Journal daily. Complete Qualtrics surveys daily. Earn gift cards.	Interview with research staff, Qualtrics survey. Interview with research staff, Qualtrics survey.	Interview with research staff, Qualtrics survey. After this interview, control group is mailed copy of journal with instructions for . Telephone interview with research staff, Qualtrics survey.

Detailed description of the activities of the treatment group. There are three phases to this intervention: the Group Phase (8 hours of content), the Independent Practice Phase (2 week duration after the group terminates in which participants practice PPJ 3-7 times per week), the Qualitative Exit Interview, which features the final quantitative Qualtrics questionnaire and an in-depth semi-structured exit interview to ascertain satisfaction with and criticism of PPJ, study logistics and the Follow-Up interview 30 days later which is a brief interview and final Qualtrics survey. We will encourage completion of the quantitative Qualtrics questionnaire before the exit interview facilitated by research staff for all research participants. Participants continue with treatment as usual during PPJ study activities.

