"We will not ask you about child or vulnerable adult abuse. If you tell us about child or vulnerable adult abuse or neglect, we may have to report it to authorities because of law or policy. This is true if you tell us in group, one on one meetings, or in journal entries. Also, if we learn (in person or in any other contact you have with us) that you are at risk for hurting yourself or others, we will inform NUWAY treatment staff of this information as soon as possible.

"In general, if something worries us about what you share with us in any way, we will let NUWAY staff know. This includes any time you tell us that you have used drugs or alcohol. Telling us that you have used drugs or alcohol will have the same consequences as if you told a NUWAY staff member that you used drugs or alcohol. NUWAY staff would work with you to make sure that you have the support you need to get back on track related to your recovery.

"If you tell us that you committed a crime, we would tell NUWAY Staff. Telling us that you committed a crime would have the same consequences as if you told a NUWAY staff member that you committed a crime. If you are on probation or parole, NUWAY staff would need to report this to your probation or parole officer.

"If you tell us that you intend to hurt yourself or someone else, we would tell NUWAY staff.

"Some of these things that you might tell us might have consequences related to your treatment status at NUWAY.

"In general, the NUWAY Staff will not find out your answers to the iPad surveys."

11. Number of Participants

11.1. Number of participants to be consented will be approximately 100.

12. Recruitment Methods

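### Uncontrolled pre-post change is used to read the mediators, and the between-arm tests have no stated error control

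*Combined protocol and SAP*

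**What the plan says.** The analysis is described in two places.

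- **Section 5.2, Analysis Plan, secondary measures.** Pre-post means and standard deviations of the hypothesised mediators are examined "to determine if change is in the expected direction". No comparator is named in that sentence.
- **Section 5.2, Analysis Plan, comparison of groups.** After conceding low power, the plan states: "we will compare differences between the treatment and control groups at baseline and over time using either t-tests or multi-level modeling". It adds that t-tests will show significant group differences and that multi-level models will show whether rates of change differ significantly between groups.
- **Section 17.3.** Arms are compared by t tests *and* multi-level models, on means and slopes respectively. A further sentence, opening with *Also*, says multi-level analyses will "be conducted to determine significant change over time in factors of interest". It does not mention arm.

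The Study Activities by Arm table in Section 5.2 says: "All participants continue with treatment as usual at the host setting throughout this study". Neither section gives an alpha for the mediator tests, a key mediator, a key time point or a multiplicity rule. Alpha appears only in the power calculation (Section 17.2), in two versions: one-tailed .10 and two-tailed .05.

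**The concern.** The trial has a randomised control arm so that PPJ can be separated from everything else happening to people in early recovery. A test of change over time without arm gives that up, and so does a check that pre-post change runs the right way.

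The protocol itself gives reasons to expect improvement without PPJ. Clients at the main site receive 20 hours of treatment a week (Section 23.1). Some early discomforts are expected to subside as treatment goes on (Section 16.1). Earlier participants found that completing the mood scale was itself therapeutic (Section 16.1), and both arms complete that scale repeatedly. The one-arm development phase already reported significant pre-post gains on this logic (Section 2.2, Relevant Study #3).

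The second issue is error control. Many self-report scores at several time points, with two candidate methods and no stated rule, will yield some significant arm differences by chance. Baseline tests add more, and after randomisation a baseline difference is chance by construction. At stake is whether a reader of the results can tell a PPJ signal from recovery under usual care, or from chance.

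**Working it through.** **1. The plan's own figures.** The plan states no test count and no family-wise error rate. Its only error levels belong to the power figures in Section 17.2, where behavioural activation data "was used to determine power for the original proposal with N=76". Allocation is "randomized into treatment and control groups using randomly generated pairs of numbers" or by REDCap; I take 1:1, so 38 per arm. With h = 2·arcsin√p1 − 2·arcsin√p2 and power = Φ(h·√(n/2) − z):

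- Abstinence, 41.5% v 24.8%: .609 at one-tailed .10 and .344 at two-tailed .05. The plan gives .61 and .34 ("for a 2-tailed test with $p < .05$, power would be .34").
- Retention, 96.6% v 75.9%: .942 and .815. The plan gives .94 and .82.

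These reproduce, but they concern the two binary outcomes. Using .05 for the mediators is my assumption.

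**2. Change over time with no PPJ effect.** Section 11.1 gives the sample: "Number of participants to be consented will be approximately 100". I use n=100 with no dropout. Natural improvement d (in SD units) and pre-post correlation r are assumptions. The standardised change is dz = d/√(2(1−r)), the noncentrality is dz·√n, and the test is a two-sided paired t at .05.

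| d | r | dz | noncentrality | chance of significance |
|---|---|---|---|---|
| 0.1 | 0.5 | 0.100 | 1.00 | 17% |
| 0.1 | 0.7 | 0.129 | 1.29 | 25% |
| 0.2 | 0.5 | 0.200 | 2.00 | 51% |
| 0.2 | 0.7 | 0.258 | 2.58 | 72% |
| 0.4 | 0.5 | 0.400 | 4.00 | 98% |
| 0.4 | 0.7 | 0.516 | 5.16 | 99.9% |

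With n=76, as an illustration of dropout, the range for d = 0.2 to 0.4 is 41% to 99%. The chance that observed change merely has the expected sign, Φ(noncentrality), is 98% or more at n=100 for d of 0.2 or above.

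**3. Number of between-arm tests.** Table 2 in Section 5.2 marks these self-report scores at all three post-baseline points (end of Phase 1, end of Phase 2, final activities including the one-month follow-up): PANAS positive, negative and serenity; self-efficacy; commitment (single item and full scale); alcohol craving; drug craving; happiness with recovery; life satisfaction; quality of life; flourishing; HADS anxiety and depression; trait gratitude; treatment satisfaction. That is 16. The PPJ-specific single items are left out because their number is not given.

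Expected false positives = k × .05, whatever the correlation:

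- One slope per score: 16 × .05 = 0.8.
- A t-test at each time: 16 × 3 = 48; 48 × .05 = 2.4.
- Both, as Section 17.3 can be read: 48 + 16 = 64; 64 × .05 = 3.2.

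The chance of at least one does depend on correlation. Simulating with assumed correlations of 0.2 to 0.6 between scores and 0.5 to 0.7 between times gives 32% to 52% for 16 tests and 57% to 85% for 48. At one-tailed .10, the other level in Section 17.2, the expected counts double.

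**The case against.** The strongest reply is that the right analysis is already planned. Both sections compare slopes between arms, which is the arm-by-time contrast. That stands, and a reader should not infer that the plan ignores the control arm. The absence of arm from the extra change-over-time analysis is inferred from one unspecified sentence. I read it that way because the sentence is added after between-arm slopes have been covered.

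A reader might also infer that the plan tests 48 arm differences at 5%. The documents do not say so. Forty-eight needs a separate t-test at each time point, Section 5.2 offers t-tests *or* models, and no alpha is set. The count is a range.

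The pre-post sentence in Section 5.2 is descriptive and names no test; it sits beside checks on variability and on floor and ceiling effects. Also fair: detecting real natural improvement is not a false positive. The error would lie in attributing it to PPJ, which no section says outright. Uniform improvement is doubtful too. Commitment to sobriety was near ceiling and did not rise in the earlier phase (Section 2.2), and one study cited in Section 2.3 found no change in trait gratitude.

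Finally, this is a pilot whose main objective is feasibility and acceptability, and it calls itself underpowered. That lowers the stakes. It does not answer the point, because low power concerns missed effects, whereas the plan's wording on significance concerns claimed ones.

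**Conclusion.** The point holds in a limited form. Sections 5.2 and 17.3 place an uncontrolled reading of mediator change beside a valid between-arm one and do not say which carries the conclusion. The uncontrolled reading cannot distinguish PPJ from usual treatment, natural recovery or repeated assessment. Under an assumed 0.2 to 0.4 SD natural improvement (r 0.5 to 0.7, n=100, no dropout), the pooled test would be significant about 51% to 100% of the time with no PPJ effect; at 0.1 SD, 17% to 25%. The between-arm tests number about 16 to 64, with roughly 1 to 3 false positives expected at an assumed .05 if PPJ affects none of these scores.

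It would go too far to say that spurious significance will drive the larger trial. Section 17.3 sends descriptive statistics, not these test results, to its power and sample size calculations. The harm is to interpretation of the pilot's mediator findings.

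**What to change.** In Sections 5.2 and 17.3:

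1. State that any conclusion about mediators rests on the between-arm (arm-by-time) contrast already planned.
2. Keep within-arm and pooled pre-post change as description only, with no significance test and no criterion based on the direction of change.
3. Report between-arm mediator differences as exploratory estimates with 95% confidence intervals, without significance claims, and make the two sections agree on the method.
4. Tabulate baseline characteristics by arm without tests.

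Naming one key mediator and time point is optional in a pilot of this kind. The change is to analysis wording only and needs no new data. The cost is fewer significant results to report.
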